2.4 Secondary endpoints

- Overall survival (OS), response rate (RR), adverse events (AE) and serious adverse events (SAE) rate

3 Overall study design

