3.1 Type of study

This is an open label, single-arm, multicentre phase II trial evaluating the maintenance treatment of oral lenalidomide monotherapy given to patients with relapsed DLBCL who presented at least a PR to a second- or third-line therapy.

A total number of 47 eligible patients will be enrolled in the protocol and receive Lenalidomide 25 mg for 21 days every 28 days, until clinical appropriate. These subjects will be continuously monitored for safety, disease status and survival.

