6.2 Safety measures

6.2.1 Adverse events

6.2.1.1 Adverse Event Definitions and Classifications

Timely, accurate, and complete reporting and analysis of safety information from clinical studies are crucial for the protection of subjects and investigators and are mandated by Regulatory Agencies worldwide.

- *Adverse Event*

An adverse event (AE) is any untoward medical occurrence in a clinical investigation subject administered a pharmaceutical product. An adverse event does not necessarily have a causal relationship with the treatment. An adverse event can therefore be any unfavorable and unintended sign (including an abnormal laboratory finding), symptom, or disease temporally associated with the use of an investigational medicinal product, whether or not considered related to the investigational medicinal product (Definition per International Conference on Harmonization [ICH]).

This includes any occurrence that is new in onset or aggravated in severity or frequency from the baseline condition, or abnormal results of diagnostic procedures, including laboratory test abnormalities.

Note: The Investigator collect adverse events starting from the time of signing the informed consent through the end of the designated follow-up period.

Abnormal laboratory values defined as adverse events

An abnormal laboratory value is considered to be an AE if the laboratory abnormality is characterized by any of the following:

- results in discontinuation from the study
- requires treatment, modification/interruption of study drug dose, or any other therapeutic intervention
- is judged by the Investigator to be significant clinical importance

If a laboratory abnormality is one component of a diagnosis or syndrome, then only the diagnosis or syndrome should be recorded on the AE page of the CRF. If the abnormality was not part of a diagnosis or syndrome, then the laboratory abnormality should be recorded as the AE.

- *Serious Adverse Event*

A serious adverse event (SAE) as defined by ICH is any untoward medical occurrence that at any dose:

- results in death
- is life-threatening (the subject was at risk of death at the time of the event. It does not refer to an event that hypothetically might have caused death if it were more severe).
- results in persistent or significant disability/ incapacity, or
- is a congenital anomaly/birth defect

OSPEDALE SAN RAFFAELE
ISTITUTO DI RICOVERO E CURA A CARATTERE SCIENTIFICO

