Note: Medical and scientific judgment should be exercised in deciding whether expedited reporting is also appropriate in situations other than those listed above. For example, important medical events may not be immediately life-threatening or result in death or hospitalization, but may jeopardize the subject or may require intervention to prevent one of the outcomes listed in the definition above. Any adverse event is considered a serious adverse event if it is associated with clinical signs or symptoms judged by the investigator to have a significant clinical impact. Events not considered to be SAEs are hospitalizations which: were planned before entry into the clinical study; are for elective treatment of a condition unrelated to the studied indication or its treatment; occur on an emergency outpatient basis and do not result in admission (unless fulfilling other criteria above); are part of the normal treatment or monitoring of the studied indication and are not associated with any deterioration in condition.

If an AE is considered serious, both the AE pages of the CRF and the SAE Report form must be completed.

For each SAE, the investigator will provide information on severity, start and stop dates, relationship to (investigational product) study drug, action taken regarding (investigational product) study drug and outcome.

- *Classification of severity*

For both AEs and SAEs, the investigator(s) must assess the severity of the event. The severity of adverse events (AEs) will be graded on a scale of 1 to 5 according to the National Cancer Institute (NCI) Common Terminology Criteria for Adverse Events Version 3.0 (NCI CTCAE). The NCI CTCAE V3.0 can be viewed on-line at the following NCI web site: <http://ctep.cancer.gov/reporting/ctc.html>. If a specific event is not included in the NCI CTCAE toxicity scale, the following scale should be used to grade the event

Grade Definition:

- 1 **Mild** Awareness of sign, symptom, or event, usually transient, requiring no special treatment and generally not interfering with usual daily activities
- 2 **Moderate** Discomfort that causes interference with usual activities; usually ameliorated by basic therapeutic manoeuvres
- 3 **Severe** Incapacitating with inability to do usual activities or significantly affects clinical status and warrants intervention. Hospitalization may or may not be required
- 4 **Life-threatening** Immediate risk of death; requires hospitalization and clinical intervention.

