If an adverse event considered associated with the study medication results in a patient's death, then the event will be listed as a "treatment-related mortality".

Procedures

All Adverse Events

All AEs, with the exception of progression of systemic AL-amyloidosis, that occur between the first study-related procedures and for 30 days following the last dose of investigational product will be reported. Resolution information after 30 days should also be provided for grade 3 to 4 drug related events. This subset should be followed up until resolution to a grade 1 or better.

Adverse events occurring after 30 days should also be reported if considered related to investigational product.

Clinically relevant changes in laboratory values must be recorded in the adverse event section of the CRF.

All AEs, regardless of seriousness, severity, or presumed relationship to study therapy, must be recorded in the source document and the CRF. Investigators must record in the CRF their opinion concerning the relationship of the adverse event to the study therapy. All measures required for adverse event management must be recorded in the source document.

The Principal Investigator assumes responsibility for appropriate reporting of adverse events to the regulatory authorities. The Principal Investigator must report these events to the appropriate Institutional Review Board (IRB) that approved the protocol unless otherwise required and documented by the IRB.

Serious Adverse Event (SAE) Reporting Report of Adverse Events to Regulatory Authorities and the Ethics Committee

The sponsor will inform relevant Regulatory Authorities and the Ethics Committee:

- of all relevant information about serious unexpected adverse events suspected to be related to the study medication that are fatal or life threatening as soon as possible, and in any case no later than seven days after knowledge of such a case. Relevant follow-up information for these cases will subsequently be submitted within an additional eight days.
- of all other serious unexpected events suspected to be related to the study medication as soon as possible, but within a maximum of fifteen days of first knowledge by the investigator.

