8.5 Safety analysis

All subjects who receive at least one week of study drug medication will be included in safety analysis. AEs, vital signs measurements, clinical laboratory information and concomitant medications will be tabulated and summarized. Subject incidence rates of all AEs and events requiring the discontinuation of study drug will be tabulated by system class, preferred term, and severity using MedDRA terms and NCI-CTCAE Version 3.0 severity grades. Time to first dose reduction will be summarized for each regimen. Death and clinically important AEs (including tumour lysis and thrombosis) will also be summarized.

All other measurements will be summarized using means, standard deviations, medians, minimum and maximum. Graphical display will be provided where useful in the interpretation of results.

9 Data handling and record keeping

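### The adverse-event reporting rule exempts progression of AL-amyloidosis instead of the lymphoma under study, so DLBCL progressions, read literally, enter the crude AE tables

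*Combined protocol and SAP*

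**What the plan says.** The reporting rule is in section 6.2.1.1, under the procedures for all adverse events. It covers "All AEs, with the exception of progression of systemic AL-amyloidosis", occurring between the first study-related procedure and 30 days after the last dose. The population, in section 3.1, is "patients with relapsed DLBCL who presented at least a PR to a second- or third-line therapy".

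The AE definition earlier in 6.2.1.1 is broad. It takes in any unfavourable sign, "symptom, or disease temporally associated with the use of an investigational medicinal product, whether or not considered related to the investigational medicinal product". It adds: "This includes any occurrence that is new in onset or aggravated in severity or frequency from the baseline condition".

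An event is serious if, among other criteria, it "results in death". A later note widens this: "Any adverse event is considered a serious adverse event if it is associated with clinical signs or symptoms judged by the investigator" to matter clinically. Section 6.2.1.2 has SAEs reported whatever their attribution.

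On the analysis side, section 2.4 lists "adverse events (AE) and serious adverse events (SAE) rate" among the secondary endpoints. Section 8.5 states: "Subject incidence rates of all AEs and events requiring the discontinuation of study drug will be tabulated", broken down by system class, preferred term and severity. Section 8.3.1 names grade 3-4 events as the safety endpoint.

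**The concern.** A clause of this kind normally keeps progression of the disease under study out of adverse-event reporting, because progression is already captured as efficacy. Here the clause names a disease that the trial does not study, so it exempts nothing relevant and leaves DLBCL progression reportable. This is an operative rule that decides what reaches the AE tables.

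At stake is the meaning of the crude AE and SAE rates. With no control arm, a rate that combines drug toxicity with lymphoma progression cannot be corrected by comparison with untreated patients. The trial is also multicentre. A centre that reads the clause as written and a centre that assumes lymphoma was meant would report different events for the same clinical course. The documents do not show whether this has happened.

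**Working it through.** The plan states no expected AE or SAE rate, so there is no figure to reproduce. The check is mainly textual.

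**Step 1: is DLBCL progression an AE under the definition?** Section 6.2.1.1 includes disease arising during use of the drug, related or not, and worsening from baseline. Progression from PR, or relapse from CR, fits both.

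**Step 2: does anything else exempt it?** The only other disease-related carve-out in 6.2.1.1 concerns hospitalizations that belong to routine care of the indication and involve no deterioration. Progression is a deterioration, so the carve-out does not reach it. Sections 6.2.1.2, 8.3.1 and 8.5 contain no exemption for lymphoma progression or lymphoma death.

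**Step 3: does the tabulation filter it out?** Section 8.5 tabulates all AEs by class, term and severity, not by attribution. Marking a progression as unrelated does not remove it from the crude incidence.

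**Step 4: which outputs are exposed?**

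| Output | Exposed? | Reason |
|---|---|---|
| All-AE incidence (8.5) and AE rate (2.4) | Yes | No filter for progression |
| Events leading to discontinuation (8.5) | On a literal reading | Progression stops treatment (synopsis, 10.3), but 4.3.1 lists it apart from AEs |
| SAE rate (2.4) | In part | Only if fatal, symptomatic with clinical impact, or otherwise serious |
| Grade 3-4 AEs (8.3.1) | In part | Only progressions graded 3-4; death is grade 5 |
| Treatment-related mortality | No | Requires association with the drug |
| Expedited reports | No | Require suspicion of the drug |
| One-year PFS and the two-stage decision (8.1, 8.2.2) | No | Separate data and definition |

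**Step 5: scale.** Inputs are N = 47 and one-year PFS of 30% (null) and 50% (alternative), all from section 8.1. Section 8.2.2 counts only progression or relapse as a PFS event, so 1 − PFS is read as the share progressed.

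- Expected progressions by one year = N × (1 − PFS).
- At 50%: 47 × 0.50 = 23.5.
- At 30%: 47 × 0.70 = 32.9.

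This gives about 24 to 33 patients if both stages accrue. It is not a count of added AEs. Some progressions may occur more than 30 days after a patient stopped early for toxicity, which lowers the number. Treatment runs for 24 cycles (5.1), so progressions in the second year raise it. If the hazard were constant, an assumption, two-year progressions would be 47 × (1 − 0.50²) = 35.3 and 47 × (1 − 0.30²) = 42.8. The effect on the SAE rate would also need the SAE rate from other causes and the share of progressions that are serious. The documents give neither.

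**Step 6: where the clause came from.** Section 6.2.1.2 mentions cyclophosphamide and dexamethasone as other drugs in the study, although lenalidomide is given alone. Section 6.2.1.1 points to a Section 10.1.2 that the table of contents does not list. Both fit text carried over from another protocol, but neither proves it.

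**The case against.** The strongest reply is that the slip is obvious and the rest of the protocol keeps the two things apart. Section 4.3.1 gives lymphoma failure and discontinuation for toxicity or an adverse event as separate reasons for ending participation. Section 10.3 contrasts progression with unacceptable toxicity. Section 6.1.2 records deaths in addition to SAE reporting, and 8.5 summarises deaths separately. On that reading progression would not naturally be entered as an AE leading to discontinuation. This stands as evidence of intent, and it makes inflation of the tables a consequence of the literal text, not a certainty. It does not change the operative rule, which still exempts the wrong disease.

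Three stronger readings are tempting, and the documents do not support them.

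- A reader might infer that the safety results become uninterpretable. Attribution is recorded for each AE and tables are by preferred term, so progression entries could be identified and set aside. The exposure is in the crude totals.
- A reader might infer that the primary endpoint is double-counted. Listing a progression in a safety table does not alter one-year PFS or the two-stage decision.
- A reader might infer that the misnamed disease is what makes lymphoma deaths SAEs. The clause concerns progression in the paragraph on all AEs. SAE reporting rests on its own text in 6.2.1.1 and 6.2.1.2, which has no disease exemption, so correcting the phrase alone would not settle fatal events.

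Keeping all-cause deaths in the SAE tables, with attribution, is a defensible choice in an uncontrolled trial. That is why the fix leaves lymphoma deaths recorded and summarised.

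**Conclusion.** The point holds in a limited form. Section 6.2.1.1 exempts progression of a disease outside the trial, nothing else exempts DLBCL progression, and the AE definition covers it. Followed as written, progressions up to 30 days after the last dose enter the crude all-AE incidence and the AE-rate secondary endpoint. Some would also count as SAEs, though an asymptomatic progression is not automatically one.

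The 24 to 33 of 47 patients expected to progress by one year shows that the overlap could be large. It rests on the design's own PFS values and full accrual, and it should not be read as an upper limit on added AEs, since the 30-day window and second-year progressions pull in opposite directions. The actual inflation cannot be derived from the documents and depends on how centres applied the clause. The correction is worth making because it costs very little and protects a stated secondary endpoint.

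**What to change.** 1. In 6.2.1.1, replace systemic AL-amyloidosis with the lymphoma under study.
2. In 8.5, state that lymphoma progression is reported under efficacy and kept out of the main AE incidence and AE-discontinuation tables. If events have already been collected under the present wording, state instead that AEs and SAEs are tabulated with and without disease progression.
3. State that deaths from lymphoma are still recorded and summarised by cause, as 6.1.2 and 8.5 already foresee, and reconcile the SAE text in 6.2.1.1 and 6.2.1.2 with the corrected rule.
4. Reconcile the AE collection windows at the same time. The procedures in 6.2.1.1 end at 30 days after the last dose, with later events only if related. The note in the definitions runs to the end of follow-up, and 6.5.4 has AE reports until one year after discontinuation. The window decides which progressions are caught.

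The cost is one phrase in 6.2.1.1, a sentence or two in 8.5, and a consistency edit to the SAE and window text. Sample size, decision rule and primary analysis do not change. If data are already in, the two-way tabulation needs only a flag for progression entries.

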6.2.1.2 Immediate reporting by Investigator to Sponsor and Celgene

The investigator will inform the sponsor and Celgene of any serious adverse event. This applies to all SAEs, regardless of relationship to the study medication, that occur during the study, those made known to the Investigator(s) within 30 days after a subject's last dose of study drug, and those made known to the investigator(s) at any time that are suspected of being related to the study medication. This must be documented on an SAE form. This form must be completed in English and supplied to Celgene Europe Drug Safety within 24 hours/1 business day or at the latest on the following working day. The initial report must be as complete as possible, including details of the current illness and serious adverse event, and an assessment of the causal relationship between the event and the investigational product(s). Information not available at the time of the initial report (e.g., an end date for the adverse event or laboratory values received after the report) must be documented on a follow-up SAE form.

All adverse event reports must include the patient number, age, sex, weight, severity of reaction, relationship to study drug, date and time of administration of test medications and all concomitant medications, and medical treatment provided.

Safety Contact Information

	Safety Phone Number	Safety Fax/e-mail
Fondazione S. Raffaele Safety Desk	[contact]	[contact] [contact]
Celgene International Sarl Att. Drug Safety Department [name] 2017 Boudry CH-NE 24-H Emergency Contact Call Centre Direct [contact] and follow the instructions in the recorded message	[contact]	[contact] [contact]
Celgene S.r.l. [name] [name]	[name] [name]	[contact] [contact]

Sponsor Reporting to Celgene

The sponsor will provide Celgene with a copy of the annual safety report at the time of the submission to the regulatory authority and the Ethics Committee.

Pregnancies

Pregnancies occurring while subjects are on study drug or within 4 weeks after a subject's last dose of study drug are considered events to be reported immediately to Celgene. If the subject is on study drug the study drug is to be discontinued immediately and the subject is to be

OSPEDALE SAN RAFFAELE
ISTITUTO DI RICOVERO E CURA A CARATTERE SCIENTIFICO

instructed to return any unused portion of the study drug to the Investigator. The pregnancy must be reported to Celgene within 24 hours of the Investigator's knowledge of the pregnancy by phone and facsimile using the SAE Form. The pregnancy must also be reported to the sponsor.

The Investigator will follow the subject until completion of the pregnancy, and must notify the sponsor and Celgene of the outcome within 5 days or as specified below. The Investigator will provide this information as a follow-up to the initial pregnancy report.

If the outcome of the pregnancy meets the criteria for immediate classification as a SAE (i.e., spontaneous abortion [any congenital anomaly detected in an aborted foetus is to be documented], stillbirth, neonatal death, or congenital anomaly), the Investigator should follow the procedures for reporting SAEs. All neonatal deaths that occur within 30 days of birth should be reported, without regard to causality, as SAEs. In addition, any infant death after 30 days that the Investigator suspects is related to the *in utero* exposure to the study drug should also be reported.

In the case of a live "normal" birth, Celgene should be advised as soon as the information is available.

Any suspected foetal exposure to CC-5013 must be reported to Celgene within 24 hours of being made aware of the event. The patient should be referred to an obstetrician/gynaecologist experienced in reproductive toxicity for further evaluation and counselling.

Adverse event updates/IND safety reports

Celgene shall notify the Investigators and the sponsor via an IND Safety Report of the following information:

- Any AE associated with the use of study drug in this study or in other studies that is both serious and unexpected.
- Any AE associated with the use of any other drug in this study that is both serious and unexpected as per the Summary of Product Characteristics for cyclophosphamide and dexamethasone.
- Any finding from tests in laboratory animals that suggests a significant risk for human subjects including reports of mutagenicity, teratogenicity, or carcinogenicity.

The sponsor shall notify the EC and the relevant regulatory authorities of any new significant risks to subjects as required.

All serious adverse events that have not resolved by the end of the study, or that have not resolved upon discontinuation of the subject's participation in the study, must be followed until any of the following occurs:

- the event resolves;
- the event stabilizes;
- the event returns to baseline, if a baseline value is available;
- the event can be attributed to agents other than the investigational product or to factors unrelated to study conduct;

- when it becomes unlikely that any additional information can be obtained (subject or health care practitioner refusal to provide additional information, lost to follow-up after demonstration of due diligence with follow-up efforts).

Data protection

Patient's identity will stay anonymously.

6.2.2 Safety board

An Independent Data Monitoring Committee (IDMC) will review ongoing safety and efficacy data and at the time of the planned analyses to assess benefit-to-risk considerations throughout the study. Additional safety reviews will occur at scheduled intervals agreed upon by the IDMC.

6.3 Monitoring and prophylactic treatment for hepatitis B reactivation

At screening patients will be tested for hepatitis B serologic markers, that is HBsAg, HBsAb, and HBcAb. Patients with positive serologic markers should be tested for viral load dosing HBV-DNA. Patients with detectable levels of HBV-DNA will be excluded. Patients with HBsAg positivity, independently from HBsAb and HBcAb titres, will receive prophylaxis with lamivudine 100 mg/d. It will be started 1-2 weeks before lenalidomide treatment. HBV-DNA will be assessed on day 1 of each course (± 7 days of scheduled visit), at the end of lenalidomide (within 7 days after stopping drug), and at 28-day follow-up visit (± 7 days of scheduled visit). Patients with undetectable levels of HBV-DNA and/or with HBsAg negativity, independently from HBsAb and HBcAb titres, will not receive prophylaxis treatment; HBV-DNA will be assessed as above mentioned. Antiviral prophylaxis therapy should continue for at least 4 weeks after last dose of lenalidomide. For hepatitis B reactivation definition and management guidelines see following table.

Guidelines for management of hepatitis B

HBV reactivation (with or without clinical signs and symptoms)*	
For patients with positive HBsAg reactivation is defined as: new appearance of measurable HBV-DNA ± ALT elevation $\times 5$ ULN	Treat: Start a second antiviral AND interrupt lenalidomide administration until resolution: • \leq grade 1 ALT (or baseline ALT, if $>$ grade 1) and • undetectable HBV-DNA levels If resolution occurs within < 28 days: lenalidomide should be re-started at 10 mg/d. If the patient is already receiving 10 mg/d of lenalidomide, according to the protocol, the patient should restart at the same dose after resolution. Both antiviral therapies should continue at least 4 weeks after last dose of lenalidomide. If resolution occurs > 28 days: Patients should discontinue

	lenalidomide but continue both antiviral therapies at least 4 weeks after last dose of lenalidomide.

For patients with baseline results:
 
Negative HBsAg AND [Positive HBs Ab (with no prior vaccination against HBV), OR positive HBc Ab]
 
reactivation is defined as: New appearance of measurable HBV-DNA
	
Treat : Start first antiviral medication AND interrupt lenalidomide administration until resolution (undetectable HBV-DNA levels).
 
If resolution occurs within < 28 days: lenalidomide should be re-started at 10 mg/d. If the patient is already receiving 10 mg/d of lenalidomide, according to the protocol, the patient should restart at the same dose after resolution. Antiviral therapy should continue at least 4 weeks after last dose of lenalidomide.
 
If resolution occurs > 28 days: Patients should discontinue lenalidomide but continue antiviral therapy at least 4 weeks after last dose of lenalidomide.

* All reactivations of hepatitis B are to be recorded as grade 3 (CTCAE v 3.0 Metabolic Laboratory/Other: Viral Re-activation), unless considered life threatening by the investigator (grade 4 (CTCAE v 3.0 Metabolic Laboratory/Other: Viral Reactivation).

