4.2 Exclusion criteria

- CNS involvement

OSPEDALE SAN RAFFAELE
ISTITUTO DI RICOVERO E CURA A CARATTERE SCIENTIFICO

- Time to progression < 3 months after the previous line of treatment
- Use of experimental drugs during salvage chemotherapy
- Concomitant malignancies diagnosed in the last five years before patient's registration
- Severe concomitant illnesses / medical conditions (e.g. impaired respiratory and/or cardiac function, uncontrolled diabetes mellitus)
- Active infectious disease
- HIV positivity
- HBV-DNA or HCV-RNA positivity
- Impaired liver function (bilirubin >2 x upper normal limit; ALT/AST/GGT > 3 x upper normal limit) at one month from salvage chemotherapy conclusion
- Absolute neutrophil count (ANC) <1000/ μ L and/or platelet count <75.000 /mm³ and/or hemoglobin <9 g/dL
- Pregnant or lactating females
- Impaired renal function (creatinine clearance <50 ml/min) at one month from salvage chemotherapy conclusion
- Non-co-operative behaviour or non-compliance
- Psychiatric diseases or conditions that might impair the ability to give informed consent
- Pregnant or lactating females:

Pregnancies

Pregnancies and suspected pregnancies (including a positive pregnancy test regardless of age or disease state) of a female subject or the female partner of a male subject occurring while the subject is on study drug, or within 30 days of the subject's last dose of study drug, are considered immediately reportable events. Study drug is to be discontinued immediately and the subject instructed to return any unused portion of the study drug to the investigator(s). The pregnancy, suspected pregnancy, or positive pregnancy test must be reported to Celgene S.r.l., [contact] or [contact], [contact] or Celgene Drug Safety Department in the US at: [contact] immediately by phone and facsimile using the Pregnancy Reporting Form.

The female should be referred to a physician specialized or experienced in teratology for further evaluation and counseling.

The Investigator(s) will follow the female subject until completion of the pregnancy, and must notify the Celgene S.r.l., [contact] or [contact] or [contact] of the outcome of the pregnancy as a follow-up to the initial report.

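### Section 6.3: read literally, the and/or in the no-prophylaxis sentence withholds lamivudine from the HBsAg-positive patients the same paragraph says will receive it

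*Combined protocol and SAP*

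**What the plan says.** Section 6.3 requires hepatitis B serology at screening and an HBV-DNA test for patients with a positive marker. Four statements then decide who is enrolled and who is given prophylaxis:

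- **Exclusion.** "Patients with detectable levels of HBV-DNA will be excluded". Section 4.2 agrees, listing "HBV-DNA or HCV-RNA positivity" among the exclusion criteria. Neither place excludes HBsAg positivity.
- **Give.** "Patients with HBsAg positivity, independently from HBsAb and HBcAb titres, will receive prophylaxis with lamivudine 100 mg/d".
- **Timing.** "It will be started 1-2 weeks before lenalidomide treatment".
- **Withhold.** "Patients with undetectable levels of HBV-DNA and/or with HBsAg negativity, independently from HBsAb and HBcAb titres, will not receive prophylaxis treatment".

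The management table in 6.3 covers reactivation. For HBsAg-positive patients the instruction is "Start a second antiviral AND interrupt lenalidomide administration until resolution", and later "Both antiviral therapies should continue at least 4 weeks after last dose of lenalidomide". For HBsAg-negative patients with HBsAb (not from vaccination) or HBcAb it is "Start first antiviral medication AND interrupt lenalidomide administration until resolution".

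**The concern.** The give and withhold rules use different criteria. The first depends on HBsAg alone. The second is met by HBsAg negativity or, on the *or* reading, by undetectable HBV-DNA alone. Eligibility already requires that HBV-DNA is not detectable, so the second criterion does not separate patients within the trial, and the withhold rule reaches the group the give rule is meant to protect.

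What is at stake is patient safety and consistency between sites. The trial is multicentre. A site applying the later sentence as written would not start lamivudine in an HBsAg-positive patient, while another site applying the earlier sentence would. Under the protocol's own rules a reactivation is recorded as at least grade 3. Lenalidomide is interrupted, then restarted at 10 mg/d or stopped for good if resolution takes more than 28 days. Under 4.3.1, stopping the drug for an adverse event ends study participation.

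**Working it through.** The plan gives no figure to reproduce. The check is one of logic, followed by a rough size.

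**Step 1: apply the rules to each combination of HBsAg and HBV-DNA.**

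| HBsAg | HBV-DNA | Can be enrolled? | Give rule | Withhold rule, *or* | Withhold rule, *and* |
|---|---|---|---|---|---|
| + | detectable | no | – | – | – |
| − | detectable | no | – | – | – |
| + | undetectable | yes | give | withhold (**conflict**) | does not apply |
| − | undetectable | yes | does not apply | withhold | withhold |

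With *or*, the withhold rule covers 2 of the 2 enrollable rows and contradicts the give rule in one of them. That row holds every HBsAg-positive patient who can enter the trial. With *and*, each enrollable row has exactly one instruction.

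One group lies outside the table. Patients negative for all markers are not required to have a screening HBV-DNA result. They are HBsAg-negative, so the give rule never applies to them and they get no prophylaxis under any reading.

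**Step 2: find the intended reading.** If nobody received prophylaxis, these parts of 6.3 would have no one to apply to:

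- the lamivudine dose and its start before lenalidomide;
- the instruction to continue prophylaxis for at least 4 weeks after the last lenalidomide dose;
- the HBsAg-positive table row, where a *second* antiviral presupposes a first.

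The HBsAg-negative row starts a *first* antiviral, which fits patients who were not on prophylaxis. Both rows agree with the *and* reading.

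**Step 3: size.** The documents do not give the share p of HBsAg-positive patients among those enrolled, so a range is assumed. With N = 47 (section 8.1), the expected number is 47p and the chance of at least one is 1 − (1 − p)^47.

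| Assumed p | 47p | 1 − (1 − p)^47 |
|---|---|---|
| 0.005 | 0.24 | 1 − 0.995^47 = 0.210 |
| 0.01 | 0.47 | 1 − 0.99^47 = 0.376 |
| 0.02 | 0.94 | 1 − 0.98^47 = 0.613 |
| 0.05 | 2.35 | 1 − 0.95^47 = 0.910 |

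These are chances of enrolling an affected patient. The chance that prophylaxis is then withheld also depends on which sentence the site follows, and the documents give no basis for estimating that.

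**The case against.** The strongest reply is that no careful reader would withhold. The lamivudine sentence is explicit and specific, the literal reading empties several other instructions in the section, and *and/or* permits *and*. On this view it is a wording slip with a recoverable rule. The recoverability stands and limits the seriousness. It does not make the sentence safe. The table deals with what to do after reactivation, whereas the prophylaxis decision comes 1–2 weeks before lenalidomide. At that point the site has two opposing instructions, and the later one names its patient's own result, undetectable HBV-DNA.

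A second reply is that little time remains for the wording to matter. This version is dated 1 December 2015; the synopsis ends recruitment in December 2015 and section 3.2 in July 2013. So few or no new patients may start under this text. That reduces the reach without removing it: treatment runs for 24 cycles of 28 days (24 × 28 = 672 days), so late entrants could still be on lenalidomide.

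A third is that HBV-DNA is checked on day 1 of each course, at the end of lenalidomide and at the 28-day visit under either reading. This is true and limits harm, but the checks detect reactivation and do not prevent it.

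Finally, it is fair to say that the point is an internal inconsistency and not a disputed design choice, and that the probabilities in the size table rest wholly on assumed shares.

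**Conclusion.** The concern holds. As written, 6.3 gives opposite prophylaxis instructions for every HBsAg-positive patient who can be enrolled, and nothing elsewhere in the documents corrects it. The logical result needs no assumption beyond reading *and/or* to include *or*. The intended rule, prophylaxis for HBsAg-positive patients, can be recovered from the rest of the section, so the fault is confined to one conjunction.

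The exposed group is small: 0.2 to 2.4 expected patients out of 47 for assumed shares of 0.5% to 5%, and possibly none. The design and primary analysis are untouched. It should be fixed because it is a safety instruction that contradicts itself and the correction costs almost nothing.

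**What to change.** Limit the no-prophylaxis sentence to HBsAg-negative patients with undetectable HBV-DNA by changing *and/or* to *and*. Slightly cleaner still is to drop the HBV-DNA condition and say that HBsAg-negative patients receive no prophylaxis, which also covers those negative for all markers and not tested for HBV-DNA at screening. State that all enrolled HBsAg-positive patients receive lamivudine 100 mg/d, subject to confirmation by the sponsor's clinical team.

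Send sites a short clarification. It should ask them to check the HBsAg status and antiviral treatment of patients already on lenalidomide and to raise any HBsAg-positive patient not on lamivudine with the sponsor.

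The cost is one word or one sentence in 6.3, plus the clarification. The *first* and *second* antiviral wording in the table can stay, and the design, sample size and analysis do not change.
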